**Study protocol 09-014-07
STUDY PROTOCOL**

**Randomized study to compare the Cook Cervical Ripening Balloon plus
Pitocin to Pitocin alone in PROM patients**

Global Clinical Number 09-014

Sponsor: [name], President
Cook Research Incorporated
[name]
[name]
USA
[contact]
[contact]

Data Coordinating Center and Monitor: Cook Research Incorporated
[name]
[name]
USA
[contact]

[figure not shown]
Coordinating Clinical Investigator: [name]
Tucson Medical Center
[name]
[name]
USA
[contact]

STUDY PROTOCOL SIGNATURE PAGE

This clinical investigation will be conducted in accordance with the study protocol, 21 CFR 812, ICH-GCP, and other applicable requirements as appropriate. The protocol will be revised, as appropriate, based on new information.

Signatures:

Sponsor Contact

Signature

27 Apr 2018

DD/MM/YYYY

[name]

Printed Name

PRESIDENT

Title

Principal Investigator

I hereby confirm that I approve of this Study Protocol and agree to comply with its terms as laid out in this document.

Signature

DD/MM/YYYY

Printed Name

Title

CONFIDENTIALITY STATEMENT

This document shall be treated as a confidential document for the sole information and use of the clinical investigation team and the Institutional Review Board (IRB).

Introduction:

Cervical ripening and induction of labor continues to be a significant problem for patients with premature rupture of membranes (PROM) at term and near term with an unfavorable cervix. Despite the fact that some chemical means of effecting cervical ripening exist, their effectiveness is unpredictable in PROM patients. The purpose of this study is to compare the Cook Cervical Ripening Balloon (CRB) plus Pitocin to Pitocin alone in term and near term PROM patients not in labor.

Objectives:

To evaluate the safety and effectiveness of the CRB to expedite labor in term and near term PROM patients not in labor in conjunction with Pitocin compared to Pitocin alone.

The primary effectiveness endpoint is the time from start of labor induction to delivery.

The primary safety endpoint is the incidence of protocol-defined chorioamnionitis.

Study Design:

This is a prospective, controlled, randomized, multicenter study to compare the safety and effectiveness of the CRB plus Pitocin to Pitocin alone in term and near term PROM patients not in labor.

This study intends to enroll up to 200 patients, randomized 1:1 into two treatment groups, at up to five investigational sites.

Inclusion Criteria:

1. Intrauterine pregnancy $\geq 34 \frac{0}{7}$ and $\leq 42 \frac{0}{7}$ weeks
2. PROM not in labor
3. Bishop score ≤ 6
4. Maternal age ≥ 18 years old

Exclusion Criteria:

1. Patient unwilling or unable to provide informed consent
2. Evidence of chorioamnionitis at enrollment
3. Malpresentation (e.g., transverse fetal orientation, breech presentation)
4. History of prior cesarean section or uterine surgery
5. Major fetal anomaly or aneuploidy (anomalies that require immediate medical or surgical intervention)
6. Significant vaginal bleeding
7. Multiple gestation
8. Contraindication to vaginal delivery (e.g., placenta previa, vasa previa, placenta percreta, prolapsed umbilical cord, active genital herpes infection, invasive cervical cancer)
9. Contraindication to labor induction
10. Abnormal (Category III) fetal heart rate patterns
11. Maternal heart disease requiring medication or resulting in significant cardiac dysfunction
12. Severe maternal hypertension (chronic or preeclampsia)
13. Patient receiving or planning to undergo exogenous prostaglandin administration
14. Polyhydramnios
15. Pelvic structural abnormality that would preclude labor
16. Presenting part above the pelvic inlet (i.e., - 4 station and above)

Study Considerations:

The CRB is indicated for mechanical dilation of the cervical canal prior to labor induction at term when the cervix is unfavorable for induction. The CRB is cleared for commercial use and is routinely used in labor and delivery patients at many institutions for cervical ripening. It has been adopted over the past several years as an important method of ripening the cervix in nulliparous and multiparous women who have an indication for delivery.

Although it has been used more frequently in term or near term patients, the CRB has also been used at other gestational ages where delivery is sought in a patient who has an unfavorable cervical exam, i.e., the cervix is not ripe or is unlikely to respond to the normal labor stimulants. In many of these circumstances the contraindications to the use of this device are discounted because of the inherent benefits the device affords in achieving labor in a reasonable time period. One of these conditions is the event of rupture of membranes (ROM), which is listed as a contraindication in the CRB Instructions for Use (IFU). This contraindication is based on the idea that anything that breeches the cervix might increase a woman's risk for infection. Several devices that impose the same risk and are approved for this indication are already in use: the fetal scalp electrode, which actually attaches to the fetus, and the intrauterine pressure catheter. Both of these devices have been part of clinical practice for over 30 years. In each of these cases the device is being used during labor to improve the quality of monitoring or safety of labor.

It is known that a longer latency period, the period from ROM to delivery, increases the chance for infection in the form of chorioamnionitis, neonatal sepsis, or postpartum endometritis. It is for this reason that once ROM has occurred in the term or near term pregnancy, it is important to expedite the course of labor to avoid this infectious outcome. In the current clinical environment there are approved products and products used off-label to achieve delivery. The use of Pitocin, Cytotec[®], Cervidil[®] and the CRB have been the primary methods to achieve this goal.

Risks and Foreseeable Adverse Device Effects:

Please reference the CRB IFU for a list of adverse events that may be considered potential risks to patients participating in this study. Additional risks unique to the use of the CRB in term and near term PROM patients include intrapartum infection, adverse material reaction and entanglement of the umbilical cord.

Appropriate obstetric care and standard procedures will be used to manage the risks unique to the use of the CRB in term and near term PROM patients.

Study Procedure Initiation:

Patients meeting all inclusion criteria and no exclusion criteria will be invited to participate in the study. Patient eligibility for enrollment will be based on known information at the time of enrollment; information obtained at a later date may contradict this information but will not be considered a noncompliance with the study protocol. Patients will have the study procedures, risks and benefits explained to them and will have the opportunity to ask questions. Point of enrollment occurs when the patient is randomized into the study.

For patients who have not received any prenatal care or who, for any other reason, have not been assessed for abnormal placentation, it is recommended that an ultrasound be performed prior to study enrollment to assess the location of the placenta. Enrolled patients will be randomized 1:1 to treatment with the CRB plus Pitocin (Group A) or Pitocin alone (Group B). Randomization will utilize a computer generated randomization assignment that is stratified for parity, i.e., nulliparous and multiparous women will be accounted for in the randomization assignment. Approximately 200 pregnant women who meet the eligibility criteria will be enrolled into the study.

Both groups A and B will receive Pitocin in accordance with ACOG recommendations to be started within 90 minutes of study enrollment. Limit ambulation per site's standard of care following administration of Pitocin.

Patients randomized to Group A will undergo CRB placement within 90 minutes of study enrollment. Please reference the CRB IFU for a description of patient preparation and suggested instructions for use. In this study, the intrauterine balloon should be inflated with 60 cc of saline, and the vaginal balloon should be inflated with 30 cc of saline.

Pitocin Administration:

Pitocin will be administered in accordance with current ACOG recommendations and following institutional protocols. Details of Pitocin administration, including the maximum amount of Pitocin administered, amount of Pitocin administered at the time of delivery (prior to post-delivery bolus) and total amount of Pitocin infused, will be recorded for each patient. Providers are permitted to suspend Pitocin for periods of time at their discretion for maternal or fetal indications.

Intrapartum Procedure Management:

The CRB will remain *in situ* for up to 12 hours or until it falls out of the vagina or when it is determined that the intrauterine balloon has descended past the cervix; please reference the IFU for a description of device removal. The removal of the CRB will have no impact on the use of Pitocin, its dosage, or its continued use. Those decisions will be made based on progress of labor and institutional standard of care, and in accordance with the Pitocin Administration guidelines described above.

All other aspects of labor management will be at the discretion of the primary obstetrical provider. Patients known to be group B streptococcus (GBS) positive will receive prophylaxis in accordance with CDC guidelines. A cervical exam including Bishop score should be completed at baseline (i.e., within 90 minutes of point of enrollment and prior to start of labor induction) and every 6 hours until delivery.

The use of fetal scalp electrodes and intrauterine pressure catheters will also be at the discretion of the obstetrical provider. Women will be able to choose analgesia or regional anesthesia depending on their preference. If a spontaneous delivery is not possible the ultimate decision to deliver by an operative vaginal procedure versus cesarean section will be made by the obstetrical provider using institutional and national criteria.

Uterine activity relative to contraction frequency and cervical change will be monitored along with fetal wellbeing (e.g., fetal heart tones assessment) per the discretion of the obstetrical provider.

Statistical Considerations:

Primary Effectiveness Hypothesis

The primary effectiveness endpoint, the time from start of labor induction to delivery, will be analyzed on a per-patient basis based on the intent-to-treat population. The primary effectiveness hypothesis is that patients treated with the CRB and Pitocin will experience decreased time from start of labor induction to delivery than patients treated with Pitocin alone.

$$H_0: t_{\text{CRB + PITOCIN}} > t_{\text{PITOCIN}}$$

$$H_1: t_{\text{CRB + PITOCIN}} \leq t_{\text{PITOCIN}}$$

Where:

$t_{\text{CRB + PITOCIN}}$: Mean time from start of labor induction to delivery in patients treated with the CRB and Pitocin

t_{PITOCIN} : Mean time from start of labor induction to delivery in patients treated with Pitocin alone

The null hypothesis will be rejected in favor of the alternate hypothesis indicating that the treatment with the CRB and Pitocin is more effective than Pitocin alone at a p -value < 0.025 .

Primary Safety Hypothesis

The primary safety endpoint, the incidence of protocol-defined chorioamnionitis, will be analyzed on a per-patient basis based on the per-protocol population. The primary safety hypothesis is that patients treated with the CRB and Pitocin will experience non-inferior rates of protocol-defined chorioamnionitis than patients treated with Pitocin alone.

$$H_0: \pi_{\text{CRB + PITOCIN}} > \pi_{\text{PITOCIN}} + \delta$$

$$H_1: \pi_{\text{CRB + PITOCIN}} \leq \pi_{\text{PITOCIN}} + \delta$$

Where:

$\pi_{\text{CRB + PITOCIN}}$: Incidence of protocol-defined chorioamnionitis in patients treated with the CRB and Pitocin

π_{PITOCIN} : Incidence of protocol-defined chorioamnionitis in patients treated with Pitocin alone

δ : Margin of non-inferiority, set at 10% for this study

The null hypothesis will be rejected in favor of the alternate hypothesis indicating that the treatment with the CRB and Pitocin is as safe as Pitocin alone at a p -value < 0.025 .

Secondary Endpoints

The following secondary endpoints will be analyzed on a per-patient basis based on the per-protocol population:

- Incidence of failed induction,
- Incidence of cesarean section,
- Incidence of post-partum endometritis, and
- Incidence of cord prolapse.

For each outcome, the CRB and Pitocin will be compared to Pitocin alone, to assess for a significantly reduced rate. P -values will be adjusted using the Holm method controlling the family-wide Type I error rate at 0.05.

Additional Measures

The following additional measures will be reported:

- Time from PROM to delivery,
- Length of each stage of labor,
- Amount of Pitocin used,
- Incidence of post-partum hemorrhage,
- 1 minute, 5 minute, and 10 minute Apgar scores,

- Time from start of labor induction to delivery in patients with vaginal births,
- NICU admission rate,
- Total maternal hospital stay,
- Total newborn hospital stay,
- General cost analysis based on service utilization, and
- Maternal and newborn resource allocation.

Sample Size Calculations

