⁸ Apgar V, Holaday DA, James LS, Weisbrot IM, Berrien C. Evaluation of the newborn infant: second report. JAMA. 1958;168:1985-1988.

Score	Appearance (coloration)	Pulse (heart rate)	Grimace (reflex irritability)	Activity (muscle tone)	Respiration (breathing effort)
0	Blue or pale all over	Absent	No response	Limp	Absent
1	Blue or pale at extremities	< 100 bpm	Grimace or feeble cry	Weak, some movement	Weak or irregular
2	Pink all over	≥ 100 bpm	Cry or pull away	Active movement	Strong cry

Arrest of descent – Failure of the presenting fetal part to continue to descend during the second stage of labor despite uterine contractions and maternal effort (pushing).

Arrest of dilation – Failure of the cervix to progressively dilate despite active labor.

Bishop score⁹ – A scoring system used to help predict the success of labor induction. For this study, a standard Bishop score will be calculated using the scoring system below. No additional modifiers will be used in the calculation of the Bishop score.

Score	Dilatation	Effacement	Station	Position	Consistency
0	closed	0 – 30%	-3	Posterior	Firm
1	1 – 2 cm	40 – 50%	-2	Mid-position	Medium
2	3 – 4 cm	60 – 70%	-1, 0	Anterior	Soft
3	5+ cm	80+%	+1, +2	-	-

⁹ Bishop E. Pelvic scoring for elective induction. *Obstet Gynecol.* 1962;24:266-268.

Chorioamnionitis¹⁰ – A complication of pregnancy caused by bacterial infection of the fetal amnion and chorion membranes. A diagnosis of chorioamnionitis will include maternal fever $\geq 100.4^{\circ}\text{F}$ (38.0°C) plus at least two of the following symptoms with no other documented source of infection:

- Sustained maternal tachycardia with heart rate ≥ 100 bpm,
- Fetal tachycardia with fetal heart rate ≥ 160 bpm for at least 10 minutes,
- Foul smelling amniotic fluid,
- White blood cell (WBC) count $\geq 15,000$,
- C-reactive protein more than 2 mg/dL, or
- Uterine tenderness.

Cord prolapse – A condition that occurs when the umbilical cord descends alongside or beyond the fetal presenting part.

Dystocia – Pathologic or difficult labor, which may be caused by an obstruction or constriction of the birth passage or abnormal size, shape, position, or condition of the fetus.

Febrile – Temperature $\geq 100.4^{\circ}\text{F}$ (38.0°C).

Labor – A patient will be considered in labor if she is having regular, painful uterine contractions $\geq 6/\text{hr}$ resulting in progressive cervical effacement and dilatation.

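### The safety conclusion claims more than the chorioamnionitis test can show, and two harm endpoints are compared only for a reduction, with no planned estimate if they increase

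*Combined protocol and SAP*

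**What the plan says.** Under Statistical Considerations, Primary Safety Hypothesis, the claim to be tested is that the balloon arm has "non-inferior rates of protocol-defined chorioamnionitis", with an absolute margin of 10% and a one-sided level of 0.025. If the null is rejected, the result is to be read as "indicating that the treatment with the CRB and Pitocin is as safe as Pitocin alone".

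Under Secondary Endpoints, four outcomes are listed for the per-protocol population: failed induction, cesarean section, post-partum endometritis and cord prolapse. One sentence covers all four: "For each outcome, the CRB and Pitocin will be compared to Pitocin alone, to assess for a significantly reduced rate". P-values are "adjusted using the Holm method controlling the family-wide Type I error rate at 0.05". Whether these tests are one- or two-sided is not stated.

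Three other places bear on which way the harms might go:

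- Risks and Foreseeable Adverse Device Effects says the additional risks of using the balloon after membrane rupture "include intrapartum infection, adverse material reaction and entanglement of the umbilical cord".
- Study Considerations says longer latency "increases the chance for infection in the form of chorioamnionitis, neonatal sepsis, or postpartum endometritis". It also explains that the device's instructions list ruptured membranes as a contraindication, on the idea that "anything that breeches the cervix might increase" a woman's infection risk.
- Definitions describes cord prolapse as "A condition that occurs when the umbilical cord descends alongside or beyond the fetal presenting part", which is not the same event as entanglement.

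**The concern.** The objective covers safety as well as effectiveness, in women for whom the device's own instructions list a contraindication. A reader will take the sentence attached to the primary safety test as the answer to that objective. The test itself can say only that one infection outcome is not worse by 10 points.

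Cord prolapse and endometritis are harms, yet they are handled like the efficacy outcomes in the same list: the stated aim is to find fewer events. For endometritis the protocol gives reasons for movement either way (shorter latency could lower it, crossing the cervix could raise it). An outcome that can move in both directions calls for an estimate with an interval on both sides. None is planned. The adverse event and data collection sections describe reporting and recording but no between-arm analysis. The general list of tests for categorical variables is not tied to any safety statement.

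**Working it through.** **Inputs from the protocol.** 200 women randomized 1:1, so 100 per arm; expected chorioamnionitis 4% in each arm; margin 10 points; one-sided 0.025; power 0.80; four endpoints in the Holm family at 0.05. No rate is given for cord prolapse or endometritis, so **every count for those events below is an assumption**.

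**1. The plan's own figure.** By the normal approximation, n per arm = (1.960 + 0.842)² × 2 × 0.04 × 0.96 / 0.10² = 60.3, so 61. The plan states 62 per group. The margin and rate are therefore being read as intended, and the figure is not in dispute.

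**2. What rejection of the null shows.** The Newcombe upper 95% bound for a difference is d + √[(u₁ − p₁)² + (p₂ − l₂)²], where l and u are Wilson limits. For 4/100 these are 1.57% and 9.84%; for 6/100 the upper limit is 12.48%.

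- 4 against 4: 0 + √[(9.84 − 4)² + (4 − 1.57)²] = 6.3 points, below 10. An exact unconditional test gives p = 0.003.
- 6 (balloon) against 4: 2 + √[(12.48 − 6)² + (4 − 1.57)²] = 8.9 points, below 10. An exact score test also rejects at 6 against 4.

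So the equal-safety sentence would be triggered with half as many cases again on the balloon. That is a valid non-inferiority result, but not evidence of equality, and it says nothing about other harms.

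**3. What the planned comparison does with an increase.** Take an assumed 6 (balloon) against 0 cord prolapses per 100.

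- If the reduced-rate test is one-sided, Fisher's p = 1.00.
- If it is two-sided, Fisher's p = 0.029. The Holm multiplier is 4, 3, 2 or 1 by rank, giving at least 0.116, 0.087, 0.058 or 0.029. The result is below 0.05 only if it is the largest of the four p-values.
- The threshold depends on the test. For the first Holm step (0.05/4 = 0.0125), Fisher needs 8 against 0 (p = 0.0068; 7 against 0 gives 0.0140). The chi-square test, which General Statistical Analyses also allows, reaches it at 7 against 0 (p = 0.0071).

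Low power for rare events comes from the sample size, not from the wording. What comes from the wording is that neither reading yields an estimate of the increase.

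**4. What a two-sided interval would show.** Newcombe 95% limits at 100 per arm, in percentage points:

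| Assumed events, balloon vs control | Difference | 95% CI |
|---|---|---|
| 0 vs 0 | 0 | −3.7 to 3.7 |
| 2 vs 0 | 2 | −2.0 to 7.0 |
| 3 vs 0 | 3 | −1.2 to 8.5 |
| 4 vs 0 | 4 | −0.4 to 9.8 |
| 6 vs 0 | 6 | 1.1 to 12.5 |

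For the last row, with Wilson limits 2.78% and 12.48% for 6/100 and an upper limit of 3.70% for 0/100: lower = 6 − √[(6 − 2.78)² + 3.70²] = 1.1; upper = 6 + (12.48 − 6) = 12.5.

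**The case against.** The strongest reply is that this is shorthand. The sentence closes a section that names chorioamnionitis, states both hypotheses in its incidence and gives the margin, so an attentive reader knows what was tested. That is fair as to the hypothesis, which is correctly limited. It does not rescue the prespecified conclusion, and if the narrow meaning is intended, stating it costs nothing.

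A second reply is that a single primary safety endpoint is ordinary and other harms are weighed clinically. This largely stands. The two harms are prespecified endpoints compared by arm, adverse events are collected, and hemorrhage, Apgar scores and NICU admission are reported. A reader might infer that the plan hides an excess of harm. It does not: the rates would be seen. What is missing is an estimate of the difference with its uncertainty.

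A third reply concerns direction. A reader might infer that the protocol names cord prolapse as a device risk and then tests it the wrong way round. The risk section names entanglement, and prolapse is defined separately, so that inference is not supported. For endometritis, looking for a reduction follows the protocol's latency argument, although its infection argument points the other way.

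Finally, the 6 against 0 illustration has no support in the documents, and at 2 to 4 events against none the proposed interval also includes zero. Both statements are true, which is why the interval is offered as description and not as a test.

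**Conclusion.** The point holds as a matter of wording and reporting. The stated conclusion exceeds a test that can show only that chorioamnionitis is not worse by 10 percentage points, and an increase in cord prolapse or endometritis would be visible but has no planned estimate.

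The first part needs no assumption about rare events: it follows from the text, and 6 against 4 cases (upper bound 8.9 points) shows its size. The second part is illustrated only with assumed counts at 100 per arm; the per-protocol number may be somewhat lower.

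Two stronger readings should be resisted. The documents do not show that an excess of cord prolapse is expected, or that one of the illustrated size is likely. Nor do they show that the primary tests, the sample sizes or the Holm procedure are wrong. The correction is worth making because it changes what the trial may claim about safety at almost no cost.

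**What to change.** 1. In Primary Safety Hypothesis, replace the closing claim of equal safety with: *is non-inferior to Pitocin alone for protocol-defined chorioamnionitis within a 10-percentage-point margin*.
2. In Secondary Endpoints, keep the planned comparison and add: *cord prolapse and post-partum endometritis will also be reported by arm, in the same population, with the risk difference and an unadjusted two-sided 95% confidence interval, as safety outcomes presented alongside the primary safety result*.

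The Holm family can stay as it is. Taking the two harms out is optional; doing so would move the first step for failed induction and cesarean section from 0.05/4 = 0.0125 to 0.05/2 = 0.025, an easing of the efficacy thresholds that this point does not require.

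Cost: no extra patients, data or procedures, and no effect on the primary tests or sample sizes. The sponsor accepts a narrower safety claim. The intervals will be wide and will describe harm rather than exclude it: even with no events in either arm of 100, a difference of up to about 3.7 points remains compatible with the data.

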Cook intends to enroll 200 patients to account for those patients who might withdraw.

General Statistical Analyses

Statistical analyses will be performed using SAS® for Windows® (release 9.3 or higher) or other widely accepted statistical software. Clinically relevant baseline variables will be tabulated and compared between the treatment groups. Categorical variables will be assessed using appropriate contingency table analyses (chi-square test or Fisher's exact test) and logistic regression to assess the importance of covariates. Continuous variables will be tested using appropriate tests such as ANOVA, unpaired Student's t-test, or Wilcoxon rank-sum test, depending on variable distribution, and linear regression and repeated measure where appropriate. Survival analysis techniques such as Kaplan-Meier or Cox Proportional Hazards will be incorporated if censoring of data occurs.

Measures to be Taken to Avoid or Minimize Bias

This study is designed as a prospective, randomized, controlled clinical trial to minimize bias in both assigning patients to treatments and in analyzing the results.

Randomization

Assignment of patients to a treatment group will be by block randomization within each site and stratum. Sites will not be informed of the block size.

Missing Data

Due to the short-term follow-up of this study, a minimal amount of missing primary safety and effectiveness data is expected. Ten additional patients have been added to the required sample size to account for missing data. If necessary, multiple imputation will be used where the imputed values will be samples from the empirical distribution of the separate treatment groups.

The intent-to-treat population is defined as all patients who are randomized. The per-protocol population is defined as those patients who received the treatment as specified in their randomization.

Site-level Poolability

Poolability of data from multiple sites will be verified by examining the interaction between treatment arm and study site for the primary effectiveness and safety endpoints. Site-level poolability will be considered appropriate provided that these results are non-significant at the 0.05 level.

Adverse Event Definitions and Reporting:

Adverse events (AEs) are to be reported to the Data Coordinating Center using the appropriate case report form. In case of adverse device effects, completed forms will be submitted to the Data Coordinating Center as soon as possible upon knowledge of the event.

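### The four secondary superiority tests are planned only in the per-protocol population, so a claim of fewer cesareans or failed inductions would not rest on the full randomised comparison

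*Combined protocol and SAP*

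**What the plan says.** The plan assigns different analysis sets to tests of the same kind.

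- **Primary effectiveness (superiority), Primary Effectiveness Hypothesis:** time from start of induction to delivery "will be analyzed on a per-patient basis based on the intent-to-treat population".
- **Four secondary endpoints (superiority), Secondary Endpoints:** "The following secondary endpoints will be analyzed on a per-patient basis based on the per-protocol population". The direction is explicit: "For each outcome, the CRB and Pitocin will be compared to Pitocin alone, to assess for a significantly reduced rate". The p-values are to be "adjusted using the Holm method controlling the family-wide Type I error rate at 0.05".
- **Primary safety (non-inferiority), Primary Safety Hypothesis:** "the incidence of protocol-defined chorioamnionitis, will be analyzed on a per-patient basis based on the per-protocol population".

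The Missing Data section defines intent-to-treat as everyone randomised. It then says: "The per-protocol population is defined as those patients who received the treatment as specified in their randomization". Under Study Procedure Initiation both groups receive Pitocin, but "Patients randomized to Group A will undergo CRB placement within 90 minutes of study enrollment".

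The plan names no intent-to-treat or sensitivity analysis for the secondary or safety endpoints and gives no reason for the different sets. Criteria and Procedures for Withdrawal follows women who withdraw consent only up to that time. It also allows a woman to be removed from the study if treatment was never attempted.

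**The concern.** With a stated direction and family-wise error control, the four secondary tests can each support a claim. Holm's method deals with multiplicity. It does nothing about selection into the analysis set.

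Whether a woman received her assigned treatment is known only after randomisation. Group A has one more way to leave the set, because the balloon must be placed as well as Pitocin given. If women in whom placement does not happen differ in their risk of cesarean or failed induction, the retained Group A women are no longer comparable with Group B. A reported reduction could then come partly from who was left out, and with no all-randomised result beside it a reader could not tell.

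**Working it through.** **Inputs.** The plan has no power or error figure for the secondary endpoints, so there is none to reproduce. From the documents: 200 women randomised 1:1, so 100 per arm; four tests; Holm at 0.05. The first Holm step is 0.05/4 = 0.0125. It is taken as one-sided because the tests look for a reduction, although the plan does not state sidedness. Assumed, because the documents give no values: the event rate p, the share f of an arm excluded, and the risk ratio RR of excluded to retained women.

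**Formula.** With no device effect, an arm's overall rate p equals f·RR·r + (1−f)·r, so the rate among retained women is r = p / (f·RR + 1 − f). The affected arm keeps n = 100(1−f) women. The rejection probability is summed exactly over both binomial distributions, for the pooled z test and for Fisher's exact test.

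**Worked case.** Take p = 0.20, f = 0.10 and RR = 2 in Group A only. Then r = 0.20/(0.20 + 0.90) = 0.182 with n = 90, against 0.20 with n = 100. Excluded women have a rate of 2 × 0.182 = 36%. Type I error is 0.027 (z) or 0.017 (Fisher).

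**Type I error for cesarean, assumed rate 20% / 30%, nominal 0.0125**

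| Exclusions | z test | Fisher |
|---|---|---|
| None | 0.012 / 0.013 | 0.008 / 0.009 |
| 5% of A, twice the risk | 0.019 / 0.022 | 0.013 / 0.015 |
| 10% of A, twice the risk | 0.027 / 0.034 | 0.017 / 0.025 |
| 10% of A, equal risk | 0.013 / 0.013 | 0.008 / 0.009 |
| 10% of A, half the risk | 0.008 / 0.007 | 0.005 / 0.005 |
| 10% of B, twice the risk | 0.005 / 0.004 | 0.003 / 0.002 |
| 10% of B, half the risk | 0.020 / 0.021 | 0.013 / 0.014 |

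The same exclusions in both arms, at two to three times the risk, give 0.012-0.013 by z test.

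**Rare endpoints.** Take Group A exclusions of 5% at twofold, 10% at threefold or 20% at threefold risk. At an assumed 2% event rate the error is at most 0.0035. At 4% it is 0.011-0.015 by z test and 0.005-0.006 by Fisher.

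**Price of intent-to-treat.** Suppose the balloon halves a 20% cesarean rate only in women who receive it, and 10% of Group A, at equal risk, do not. The Group A rate is 0.90 × 10% + 0.10 × 20% = 11%, so the difference is 9 points instead of 10. Power by z test at 0.0125 is 0.32, against 0.38 per-protocol. At a 30% rate it is 0.51 against 0.60.

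**The case against.** Much of the case on the other side stands.

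- **Size.** The documents give no exclusion rate and no rate for any of the four endpoints. A reader might infer a large error from extreme inputs: 20% of Group A dropped at threefold risk with a 30% rate gives 0.17 by z test. That case implies a cesarean rate of 0.30/1.4 × 3 = 64% in the excluded women, and nothing in the documents suggests 20% non-receipt. With 5% dropped at twice the risk, Fisher's test (one of the options under General Statistical Analyses) gives 0.013-0.015, close to nominal.
- **Direction.** A reader might infer that per-protocol favours the balloon. It can, but it can equally work against it, and exclusions from Group B can move the error either way.
- **Scope.** A reader might infer that all four tests are affected alike. At low event rates there is little or no inflation.
- **Safety.** A reader might infer that the chorioamnionitis test is unsound because it is per-protocol. Per-protocol is a conventional set for non-inferiority. At 4/100 against 4/100 the upper 97.5% score limit is 6.4%, and dropping 10 or 20 uninfected Group A women moves it only to 7.4% or 8.6%, inside the 10% margin. Only a result near the margin could change.
- **Definitions.** A reader might infer that the withdrawal section contradicts the per-protocol definition. One governs removal from the study and the other an analysis set. They do not conflict, though attempted-but-failed placement is left unclear.
- **Harm.** Endometritis and cord prolapse also bear on device safety, and intent-to-treat can dilute a harm as well as a benefit.

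None of this supplies a reason for testing superiority only in a set formed after randomisation. Uncertain direction is itself a reason to show the all-randomised result.

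**Conclusion.** The concern holds for the secondary superiority tests, mainly cesarean and failed induction. As planned, a multiplicity-controlled claim on either would not rest on the full randomised comparison, and the plan departs without explanation from its own choice for the primary superiority test. The primary effectiveness analysis is unaffected.

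The size and direction of bias cannot be derived from the documents. Under the stated assumptions, moderate higher-risk exclusions from Group A raise the 0.0125 error to 0.019-0.034 by z test, or 0.013-0.025 by Fisher. The error is nominal at equal risk. It is below nominal if the excluded women are lower-risk Group A or higher-risk Group B, and about 0.02 by z test if 10% of Group B at half the risk are excluded. The change should be made. The lack of an intent-to-treat companion for chorioamnionitis is a minor reporting gap and does not carry the point.

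**What to change.** 1. In Secondary Endpoints, make intent-to-treat (everyone randomised, as Missing Data defines it) the main analysis set for the four superiority tests, with per-protocol as a sensitivity analysis.
2. Show endometritis and cord prolapse in both sets, so that a device harm is not hidden by dilution.
3. State that women in whom no treatment was attempted stay in the intent-to-treat set despite the removal wording under Criteria and Procedures for Withdrawal.
4. State that the multiple imputation in Missing Data also covers secondary outcomes missing after withdrawal. That section discusses expected missingness only for the primary endpoints.
5. Add one sentence saying whether attempted-but-failed balloon placement counts as treatment received for the per-protocol set.
6. As a minor addition, report the chorioamnionitis analysis in the intent-to-treat population beside the per-protocol test, with the success criterion unchanged.

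**Cost.** Plan wording and a second run of the same analyses. The sample size does not change, since it rests on the two primary endpoints. Two real costs remain: the dilution of secondary effects shown above, and a few outcomes that may be missing for women who withdraw, so it would be too strong to say that the data are all already in hand.
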